5.2 Possible Side Effects of Study Medications

Prednisolone: eye irritation, swelling, pain, or redness; pressure within the eye; cataract growth; eye infection

Ofloxacin: eye irritation, swelling, pain, or redness

Tropicamide/Phenylephrine: eye irritation, swelling, pain, or redness; Eye dilation may result in temporary blurred vision, light sensitivity, and increased heart rate.

6. PROTECTION OF HUMAN SUBJECTS

6.1 Institutional Review Board Approval

6.1.1 *Oregon Health & Science University Institutional Review Board (OHSU IRB)*

The OHSU IRB will annually review study protocol for ethical approval.

6.1.2 *University of California, San Francisco Committee on Human Research (UCSF CHR)*

The UCSF CHR will annually review study protocol for ethical approval.

6.1.3 *Stanford University Institutional Review Board (Stanford IRB)*

The Stanford IRB will annually review study protocol for ethical approval.

6.2 Informed Consent

OHSU and Stanford personnel will obtain full written consent from each patient enrolled. The primary surgeon will screen participants and determine their eligibility. He/she will clearly explain the process and risks involved and will also ask the patient to sign any necessary consent documents. The study participant will have 6 visits total per eye included in the study; visits include surgery and will take place over a period of 2 years. The patient has the ability to withdraw at any time and will not be forced into anything with which he/she is not comfortable. Consent documents have been uploaded to the IRB application.

6.3 Risks to Study Participants

Study participants will not have any increased risk or cost for participating in this study. Participants in the study have the same risks as those undergoing corneal transplantation in other settings. Many of the risks in this study are inherent risks of corneal transplantation; thus, there is no known increased risk associated with participation in this study.

As with any surgery, there are risks associated with these surgeries, and both surgeries have similar risks. There is a risk of infection or bleeding which could result in vision loss. There may be damage to the tissue graft during tissue preparation, and the tissue graft can fail to attach to the cornea; thus, there may be a need for repeat air injection. Below, the other risks associated with each type of surgery are listed:

- **DSAEK:** There may be slightly decreased vision after surgery compared to DMEK, although this is unknown. The healing process may also be slower. Some think there is an increased risk of rejection compared to DMEK, although this is also unknown.

- DMEK: There may be increased risk of tissue loss, repeat air injection, detachment of the tissue graft to the cornea compared with DSAEK. There may be higher costs associated with this surgery, although these additional costs will be covered by insurance.

Blindness due to infection may occur in extremely rare cases. There may also be differences in rates of difficulty with donor preparation, increased intra-operative times, graft rejection and graft survival, and donor attachment in DMEK versus DSAEK. Even if there is a total detachment during DMEK, we will continue to move forward with secondary treatment. These risks will be addressed by OHSU by making sure all protocols are being followed thoroughly and by following up with participants after surgery.

There are no known risks directly related to the Endoserte and jones tube. There may be some discomfort during follow-up testing (BSCVA, IOP, slit lamp, Pachymeter, Pentacam, endothelial imaging and OCT testing and photo imaging inside the eye), but this will be kept to a minimum. The participant will be asked to tell the doctor if any of this testing feels painful.

Anesthesiology will be determined as per the participants needs. They will generally be awake with medications given to help them relax and feel comfortable. This is called monitored anesthesia care. Other participants may require general anesthesia care. While this is generally safe, there are small increased risks to the heart and lungs which will be discussed with the anesthesiologist. Both types of anesthesia are routinely used for DMEK and DSAEK surgeries, although generally monitored anesthesia care is the typical route.

6.4 Privacy, Confidentiality, and Data Security

All data will be stored and transferred using a secure server with de-identified information.

We will take steps to keep the participant's personal information confidential. Health information will be kept secure and separate from information which identifies participants. Upon enrollment, participants will be assigned a code that will be used instead of their name, medical record number or other personally identifying information. Electronic files for data analysis will contain only the participant code. The code will be stored at OHSU/Stanford on a secure server and will only be accessed by study personnel – the PI, study coordinator, or other member of the study team). Access to study-related patient information will be limited only to members of the study team.

Only a small number of researchers related to this study will have direct access to the participant's medical information. Paper files will be stored in locked filing cabinets in restricted access offices at OHSU. Access to data/specimens is restricted to study personnel.

Information may be released to others outside of OHSU/Stanford who are involved in coordinating or overseeing research, but information which identifies the participant will be kept secure. To ensure the success of this study, OHSU and Stanford have partnered with University of California, San Francisco (UCSF)'s F.I. Proctor Foundation, which is a center that specializes in ophthalmology research. The coordinating center at UCSF will have access to de-identified information using a code number. UCSF's role is to support OHSU and Stanford on the data analysis portion of this study and assisting with the development of consent and study-related materials. UCSF has received IRB approval to take part in this study (IRB number: 14-13728).

6.5 Exclusion of Vulnerable Populations

The following populations will not be enrolled in this study: children (18 years and under), pregnant women, decisionally impaired adults, and prisoners.

6.6 Compensation to Participants

There is no additional cost or compensation for the study participant. There will be no compensation for research-related injury.

7. DATA COLLECTION AND MANAGEMENT

7.1 Data Collection and Entry

All data will be collected using hardcopy patient forms at OHSU and Stanford during baseline and follow-up visits. De-identified data will be uploaded to a Dropbox account in order to share the data with the UCSF study coordinator. De-identified data will be input into a database using double data entry at UCSF.

7.2 Data Consistency, Validity, and Monitoring

Data monitoring reports will be prepared using STATA and Excel. If the forms are not filled out completely, the UCSF study coordinator will contact the person responsible for completing the form to provide the missing data, or clarify any inconsistent data. The OHSU and Stanford study coordinators are the only people who are authorized to add missing data or make any changes to the study forms. All changes should be made with a red ink pen, and then signed and dated.

7.3 Data Storage and Security

De-identified data will then be input into a database using double data entry at UCSF. Data will be stored at UCSF for about 10 years.

8. STATISTICAL ANALYSIS

Please see the **Statistical Analysis Plan (SAP)** for details on the statistical analysis.

10. APPENDICES

10.1 Study Forms

Please see appropriate separate documents for the study forms.

Study forms include:

- Study visit checklist
- Baseline edibility and patient form
- NEI-VFQ
- Follow-up patient form
- Final patient forms

10.2 Protocols

Please see appropriate separate documents for the study protocols.

Protocols include:

- Best Spectacle-Corrected Visual Acuity Protocol
- Eye Bank Protocol; Donor Eligibility and Assignment
- Pentacam Protocol
- Pachymetry Protocol
- Endothelial Cell Count Protocol
- Slit Lamp Photography Protocol
- Optic Coherence Tomography Protocol

Descemet's Endothelial Thickness Comparison Trial

Statistical Analysis Plan

Francis I. Proctor Foundation, University of California San Francisco
Casey Eye Institute, Oregon Health & Science University
Byers Eye Institute, Stanford University

Investigators:

[name], PhD¹
[name], PhD*²
[name]*²
[name]*³
[name], COT²
[name], MS¹

*Principal Investigator

¹Casey Eye Institute, Oregon Health & Science University, Portland, Oregon

² Francis I. Proctor Foundation, University of California San Francisco, San Francisco, California

³Byers Eye Institute, Stanford University, Palo Alto, California

DETECT Statistical Analysis Plan

Table of Contents

1. Background	1
2. Sample Size and Randomization.....	1
3. Baseline Characteristics	1
4. Primary Analysis.....	1
5. Secondary Analyses	1
6. Other Data.....	2

1. Background

Descemets Endothelial Thickness Comparison Trial (DETECT) is a randomized, double-masked, two-arm clinical trial. The purpose of this study is to determine which of two types of corneal transplant surgeries has the better visual outcome. Study participant's eyes will be randomized to one of two treatment groups – 1.) Ultrathin Descemet's Stripping Endothelial Keratoplasty (DSAEK) or 2.) Descemet's Membrane Endothelial Keratoplasty (DMEK).

2. Sample Size and Randomization

We anticipate that 25 eyes per arm would provide 80% power to detect a 0.12 logMAR difference (approximately 1.2 Snellen lines), assuming two-tailed alpha, and a standard deviation of best spectacle-corrected visual acuity (BSCVA) at 6 months of 0.12 logMAR (approximately 1.2 Snellen lines) at 6 months. Participant's eyes will be randomized using random block sizes in Microsoft Excel ([name]).

3. Baseline Characteristics

Baseline characteristics between the 2 arms will be compared using Fisher exact test for categorical variables and Wilcoxon rank sum test for continuous variables.

4. Primary Analysis

For the primary study analysis, we will compare BSCVA between the two groups at the 6-month time period (between 5-7 months) using ANCOVA, with baseline BCVA and treatment group as covariates. Statistical significance will be assessed by permutation with a two-sided alpha of 0.05. (If the correlation coefficient between baseline BCVA and 6 month BCVA has magnitude less than 0.1, we will omit the variable entirely, yielding a post-test only analysis).

As a methodological sensitivity analysis, we will conduct ANCOVA with ranks (which becomes the Wilcoxon rank sum test in the post-test only case). Model checking will be conducted for the primary analysis (and for all secondary analyses) based on analysis of residuals versus fitted values. We will conduct leave-one-out influence analysis to locate highly influential observations (a procedure we will apply to secondary analyses also). Individuals with missing six month data will be included based on last observation carried forward from the 3 month records; individuals with no follow-up data cannot be included but will be tabulated. Sensitivity analysis of missing values will be conducted to assess the range of values of missing observations that would be needed to change the results of the hypothesis test.

Protocol for measuring BCSVA is outlined in the MOP. BSCVA will be analyzed using an intent to treat analysis, with all eyes that are randomized being analyzed at 6 months regardless of subsequent surgery or graft failure. We will tabulate results by study site.

One safety analysis will be performed. No interim efficacy or futility analysis will be conducted.

5. Secondary Analyses

Key secondary outcomes

- We will analyze endothelial cell counts controlling for baseline endothelial cell count measured at the eye bank using mixed effect multiple linear regression conducted
- NEI-VFQ will be compared between the two groups with multiple linear regression, controlling for baseline VFQ.
- Three-month BCVA will be analysed using the same procedure as the primary outcome.
- A linear mixed model will be used in which both three and six month data are modeled, with a random intercept for eye, and with time, baseline BCVA, and treatment assignment as fixed effects. A graft rejection episode will be defined as loss of graft clarity due to edema with evidence of inflammation such as anterior chamber cell or keratic precipitates, and will be compared between the two groups using Fisher's exact test.
- For the purposes of this study, primary graft failure will be defined as a lack of graft clearing or need for re-graft within the first 2 months, and will be compared between the two groups using Fisher's exact test.

Supplementary secondary outcomes

- A pre-specified non-inferiority threshold is set at a 0.1 logMAR difference in visual acuity.
- We will also look at BSCVA at using a last observation carried forward (LOCF) analysis. For study participants who experience primary graft failure and must undergo re-graft, graft failure will be noted and a BSCVA will be performed prior to performing further surgery. This last observation will be carried forward as the 6 month BSCVA.
- We will conduct the Kolmogorov-Smirnoff test to compare the 6-month (BSCVA) distribution between DMEK and DSAEK arms.
- Interface haze as measured by Pentacam densitometry will be analyzed using a Wilcoxon rank sum test.
- Corneal higher-order aberrations as measured by Pentacam will be analyzed using a Wilcoxon rank sum test.
- We will also perform a cost-effectiveness analysis of the clinical trial data, according to the protocol provided in the Supplementary Cost Effectiveness Analysis Statistical Analysis Plan.

6. Other Data

Other data to be collected include manifest refraction, graft thickness as measured by OCT, pachymetry, operative times, and adverse events or complications.

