1.1 Specific Aims

- 1) **To determine whether there is a difference in best spectacle-corrected visual acuity (BSCVA) at 6 months between patients receiving ultrathin DSAEK and DMEK.** We hypothesize that the DMEK group will have improved visual acuity compared with DSAEK at 3 months, but not at 6 months. By randomizing 25 patients per arm, we anticipate 80% power to detect a one standard deviation, or approximately 1.2 Snellen lines, difference in BSCVA between the DMEK and DSAEK groups.
- 2) **To evaluate endothelial cell loss at 6 months between patients receiving ultrathin DSAEK and DMEK.** We hypothesize that there will be a difference in endothelial cell loss at 6 months between patients receiving ultrathin DSAEK and DMEK, accounting for pre-operative endothelial cell count.
- 3) **To assess the relative role of light scatter, higher-order aberrations and graft thickness on visual acuity.** We predict that there will be increased light scatter at the

graft-host interface and but no difference in posterior corneal higher-order aberrations of the central 4mm in DSAEK versus DMEK.¹⁰

While long-term outcomes such as graft rejection and survival are beyond the scope of the initial phase of this study, we anticipate we will be able to evaluate these as we follow patients at 12 and 24 months.

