3.4 Study Visits

3.4.1 Baseline Visit

During this visit, eligible patients who are enrolling for the first time will be enrolled in the study and will give consent. The baseline patient form will be completed and the NEI-VFQ will also be administered. If a patient includes a second eye in the study, they will complete an abbreviated baseline patient form for that study eye prior to surgery. They will not complete a second NEI-VFQ at the baseline visit for their second eye. Patients will also complete BSCVA, IOP, Pachymetry, and Pentacam tests at baseline.

3.4.2 *Surgery Visit*

The enrolled study participant's eye(s) will undergo either DSAEK or DMEK surgery. If both of a participant's eyes are included in the study, randomization to DSAEK or DMEK will be performed independently for each eye.

3.4.3 *Follow-Up Visits*

The follow-up patient form will be completed at each visit, for each enrolled eye. Data collected for each follow-up visit will include:

3 month follow-up: BSCVA, IOP, pentacam topography and densitometry pachymetry, optical coherence tomography, and endothelial imaging will be performed. The NEI-VFQ form will also be completed

6 month follow-up data: BSCVA, IOP, pentacam topography and densitometry pachymetry, optical coherence tomography, endothelial imaging, and slit-lamp photography will be performed.

12 month follow-up: BSCVA, IOP, pentacam topography and densitometry pachymetry, optical coherence tomography, and endothelial imaging will be performed. The NEI-VFQ form will also be completed

3.4.4 *Final Visit*

During the Month 24 final visit, the final status and follow-up patient forms will be completed. BSCVA, IOP, pentacam topography and densitometry pachymetry, optical coherence tomography, and endothelial imaging will also be performed.

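### The sample-size statement claims 80% power without giving an alpha; at the two-sided 0.05 used for the primary test, its own inputs give about 93%

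*SAP*

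**What the plan says.** SAP section 2 gives the sample-size basis: "25 eyes per arm would provide 80% power to detect a 0.12 logMAR difference (approximately 1.2 Snellen lines), assuming two-tailed alpha". The same sentence sets the SD of 6-month BSCVA at 0.12 logMAR. No number follows the word alpha.

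Protocol 1.1 (first aim) makes the same claim in standardised form: "By randomizing 25 patients per arm, we anticipate 80% power to detect a one standard deviation". It gives no alpha either, and it counts patients where the SAP counts eyes.

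The only alpha value in the two documents is in SAP section 4, for the primary ANCOVA: "Statistical significance will be assessed by permutation with a two-sided alpha of 0.05". Three other statements bear on whether the 80% can be explained:

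- SAP section 4: "No interim efficacy or futility analysis will be conducted".
- SAP section 4, on missing data: "Individuals with missing six month data will be included based on last observation carried forward from the 3 month records".
- Protocol 3.4.2, for patients with both eyes enrolled: "randomization to DSAEK or DMEK will be performed independently for each eye".

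**The concern.** Alpha is a basic input to any power statement, and without it the calculation cannot be reproduced. The natural value to supply is the 0.05 of section 4, but a one-SD difference with 25 per arm then has clearly more than 80% power. So either the figure is wrong for the planned test, or it rests on an alpha, a loss allowance or a variance that is not disclosed.

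The practical stake is what a reader can infer from the trial size. Protocol 1.1 expects no DMEK advantage at 6 months, and SAP section 5 sets a non-inferiority threshold of 0.1 logMAR. How informative a null result would be depends on the difference the trial could detect. The documents put that at 0.12 logMAR with 80% power. On their own inputs it is about 0.097 logMAR, just inside the threshold.

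**Working it through.** **Inputs**

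| Input | Value | Source |
|---|---|---|
| Eyes per arm | 25, allocated 1:1 | SAP 2; Protocol 1.3 |
| Difference | 0.12 logMAR | SAP 2 |
| SD at 6 months | 0.12 logMAR | SAP 2 |
| Alpha | none in SAP 2; two-sided 0.05 for the test | SAP 4 |
| Stated power | 80% | SAP 2; Protocol 1.1 |

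**Formula.** For a two-sample t-test with n per arm and standardised effect d = difference/SD, the noncentrality is d × √(n/2) on 2n − 2 degrees of freedom. Power is the probability that a noncentral t variate exceeds the two-sided critical value in absolute size.

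**Attempt to reproduce the 80%.** Here d = 0.12/0.12 = 1.0, the noncentrality is √(25/2) = 3.536, and df = 48.

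| Two-sided alpha | Power, noncentral t | Power, normal approximation |
|---|---|---|
| 0.05 | 93.4% | 94.2% |
| 0.025 | 88.5% | 90.2% |
| 0.01 | 79.9% | 83.1% |

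At 0.05 the stated figure is not reproduced: 93.4 − 80 = 13.4 points. A one-sided 0.05 moves further away (96.7%).

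**What would give 80%?**

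1. *A different alpha.* Solving the t formula for 80% gives alpha = 0.0101, so 0.01 fits closely. The fit depends on the formula, since the normal approximation gives 83.1% at 0.01. Neither document mentions 0.01 or an alpha split, and interim efficacy looks are ruled out.
2. *Attrition at alpha 0.05.*

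| Evaluable eyes per arm | Power for 0.12 logMAR | Difference detectable at 80% power |
|---|---|---|
| 25 | 93.4% | 0.097 logMAR (0.81 SD) |
| 22 | 90.0% | 0.104 logMAR |
| 20 | 86.9% | 0.109 logMAR |
| 17 | 80.7% | – |
| 16 | 78.1% | – |

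   Reaching about 80% takes a loss of 8 of 25 eyes per arm (32%). No allowance is stated. Because an eye with a 3-month value stays in the analysis, those 8 eyes would need to have no follow-up data at all.
3. *A larger SD.* Power of 80% for 0.12 logMAR needs d = 0.809, so SD = 0.12/0.809 = 0.148. The plan states 0.12.

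**Does the planned analysis lower the power?**

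- *Baseline adjustment* raises it. With df = 47 and the effect divided by √(1 − r²), assumed baseline to 6-month correlations of 0.1, 0.3 and 0.5 give 93.6%, 95.2% and 97.9%.
- *The permutation test* makes little difference. In 3,000 simulated trials without the covariate, power was 92.8% (Monte Carlo SE 0.5 points). Permutation ANCOVA at an assumed r = 0.3 gave 95.2%.
- *Ranks*, planned only as a sensitivity analysis, give 92.3% at a relative efficiency of 0.955 and 89.6% at 0.864.
- *Two eyes per patient.* A design effect of about 1.5 to 1.6 would be needed. Because eyes are randomised independently, pairs split between arms offset pairs that fall in the same arm. Simulations assuming 10 to 25 bilateral patients and between-eye correlations of 0.5 and 0.9 stay at 93–94%.

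**The case against.** The strongest reply is that no miscalculation has been proved. The sample-size sentence has no alpha, the 0.05 is brought in from another section, and at 0.01 the stated inputs give 79.9%. The calculation may have been correct with its alpha unprinted. A number could also have been lost when the PDF was turned into text, although no redaction is visible at that point. Authors also often quote 80% as a floor that tacitly covers losses, and the sentence is worded as an expectation. Finally, the consequence is small: the test alpha is fixed clearly in section 4, so type I error is unaffected, and the trial has more power than it claims.

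Part of this stands. The documents do not show whether the fault is a wrong figure or a missing input, and the low consequence is conceded. It does not remove the discrepancy. If 0.05 was lost from the sentence, 80% is still not what the inputs give. If 0.01 was lost, the trial was sized at one alpha and will be tested at another, without explanation. A tacit loss allowance would have to be about a third of the eyes, which is too much to leave unstated. The correlations and numbers of bilateral patients used above are assumptions, not figures from the plan. They serve only to show that these features do not account for the gap.

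**Conclusion.** The point holds. The stated 80% does not follow from the plan's own inputs at the only alpha the plan gives. Power is 93.4% at two-sided 0.05, assuming an unadjusted t-test, 25 evaluable eyes per arm and independent eyes. Equivalently, 80% power corresponds to about 0.097 logMAR. The alpha is also not stated where it is needed.

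The discrepancy is in the safe direction: power for 0.12 logMAR remains 86.9% even with 20 evaluable eyes per arm. It does not affect the validity of the primary test or the number to enrol. It is a correction to a pre-specified figure that appears in both documents. Which input was intended cannot be determined from them.

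**What to change.** In SAP section 2 and Protocol 1.1, state the alpha and any loss allowance actually used for the sample size.

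- If alpha was 0.05 with no loss allowance, replace the claim with, for example: *25 eyes per arm gives about 93% power to detect 0.12 logMAR (SD 0.12), or 80% power to detect about 0.097 logMAR, at two-sided alpha 0.05, unadjusted, assuming complete data and independent eyes.*
- If a loss allowance was intended, give it and the resulting number of evaluable eyes, and square it with the carry-forward rule in SAP section 4.
- If another alpha was intended, give it and explain how it relates to the 0.05 of SAP section 4.

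Use eyes as the unit in both documents.

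In the first two cases the cost is wording in two places, with no change to enrolment, alpha or analysis. In the third, the sponsor must also settle which alpha governs the primary test.

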1.3 Study Design

Descemets Endothelial Thickness Comparison Trial (DETECT) is a randomized double-masked, two-arm clinical trial. The purpose of this study is to determine differences in visual outcomes between two types of corneal transplant surgeries. There will be 1:1 randomization to one of two treatment groups – 1.) Ultrathin Descemet's Stripping Endothelial Keratoplasty (DSAEK) OR 2.) Descemet's Membrane Endothelial Keratoplasty (DMEK). The enrollment period is 24 months.

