3.2.2 Eligibility criteria for study participants

Only those who meet all of the inclusion criteria and none of the exclusion criteria will be enrolled in this study.

Inclusion Criteria:

- Damaged or diseased endothelium from Fuchs or Pseudophakic Bullous Keratopathy
- Good candidates for corneal transplantation for either DMEK or DSAEK
- Willingness and ability to undergo a cornea transplantation
- Willingness to participate in follow-up visits

Exclusion Criteria:

- Participants who are decisionally and/or cognitively impaired
- Participants who are not suitable for the DMEK or DSAEK surgeries
- Prior Endothelial Keratoplasty (EK) or any other ophthalmic surgery except uncomplicated cataract surgery

- Indication for surgery that is not suitable for EK (e.g. keratoconus, stromal dystrophies and scars)
- Presence of a condition that increases the probability for failure (e.g., heavily vascularized cornea, uncontrolled uveitis)
- Other primary endothelial dysfunction conditions including posterior polymorphous corneal dystrophy and congenital hereditary corneal dystrophy
- Aphakia, or anterior chamber IOL in study eye prior to or anticipated during EK
- Planned intraocular lens exchange of an anterior chamber IOL with a posterior chamber IOL in study at time of study EK
- Pre-operative central sub-epithelial or stromal scarring that the investigator believes is visually significant and could impact post-operative stromal clarity assessment
- Peripheral anterior synechiae (iris to angle) in the angle greater than a total of three clock hours
- Hypotony (Intraocular pressure <10mmHg)
- Uncontrolled (defined as intraocular pressure >25mmHg) glaucoma
- Visually significant optic nerve or macular pathology

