3.3 Randomization

Each study eye will be randomly assigned to the 1) DSAEK or 2) DMEK treatment group. Block randomization will be performed using a computer program (Statistical package R; Version 2.12; R Foundation for Statistical Computing, Vienna, Austria) by the coordinating site.

Once an eye is enrolled in the study, the study coordinator will assign the study participant's eye an ID (alpha-numeric code) and inform the eye bank (Note: The eye bank will assign tissue to the study participant prior to knowing which arm the study participant is assigned to). The eye bank will then sign into the Dropbox account associated with this study, open the "New Patient" folder, and then open the file named with the particular study participant ID.

Once the eye bank has opened the file, the study eye has been assigned a study participant ID and randomized to treatment group; therefore, they will be included in the intention to treat analysis. (Note: See eye bank protocol for full donor tissue procurement and assignment information).

The treatment assignment will not contain identifiable patient information and will be shared using a password that is only known by the eye bank. The eye bank may only open the document for a given study participant and not for past or future study participants. The treatment assignment document should be moved from the "New Patients" folder to the "Old Patients" folder once opened.

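### Diagnosis (Fuchs versus pseudophakic bullous keratopathy) is neither a named stratum nor a covariate, so the primary comparison may lose some precision and is open to chance imbalance in this one trial

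*SAP*

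**What the plan says.** Protocol section 3.2.2 admits two indications: "Damaged or diseased endothelium from Fuchs or Pseudophakic Bullous Keratopathy". Each eye's diagnosis must therefore be settled before randomisation. The expected mix is not given.

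On allocation, Protocol section 1.3 says "There will be 1:1 randomization to one of two treatment groups", Protocol section 3.3 says "Block randomization will be performed using a computer program", and SAP section 2 says "Participant's eyes will be randomized using random block sizes in Microsoft Excel". None of these names a stratification factor.

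SAP section 4 makes the primary comparison "using ANCOVA, with baseline BCVA and treatment group as covariates". If baseline and 6-month acuity correlate at less than 0.1 in magnitude, "we will omit the variable entirely, yielding a post-test only analysis". On inference: "Statistical significance will be assessed by permutation with a two-sided alpha of 0.05".

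The supporting analyses in section 4 are rank ANCOVA, residual checks, leave-one-out influence, missing-data sensitivity and a tabulation by site. In section 5, the 3-month analysis repeats the primary procedure. The 3- and 6-month mixed model has time, baseline acuity and treatment as fixed effects. The cell-count model adjusts for the eye-bank (donor) count. No analysis includes diagnosis or is split by it.

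**The concern.** A primary endothelial dystrophy and endothelial failure after cataract surgery may reach different 6-month acuity from the same baseline acuity. If so, the planned model leaves that difference in the residual variance. With about 50 eyes the rarer diagnosis may be only a handful, and blocking alone does not balance it between arms.

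Baseline acuity is a partial safeguard. It removes only the part of a disease difference that runs through baseline acuity, and the correlation rule can drop it. The baseline comparison in SAP section 3 triggers no adjustment. If an imbalance appears and diagnosis is added only then, the choice is open to challenge as data-driven.

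**Working it through.** **The plan's own figure.** SAP section 2 claims 80% power with 25 eyes per arm, a difference of 0.12 logMAR and an SD of 0.12. The sentence says only "assuming two-tailed alpha", with no value. At two-sided 0.05 a t-test needs 17 eyes per arm for 80% power, and 25 per arm gives 93.4%. The stated 80% does not reproduce at that alpha. That is a separate point, but it means precision is not short on the SAP's own inputs.

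**Inputs.** From the documents: 25 eyes per arm, SD 0.12 (variance 0.0144), target 0.12. Assumed, because the documents give neither: bullous keratopathy share q of 10% or 20% (5 or 10 of 50 eyes), and gap g of 0.05 to 0.20 logMAR between diagnoses at equal baseline acuity. I also take the 0.12 as already mixing both diagnoses, and treat eyes as independent.

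**Chance imbalance.** With 5 such eyes among 50 and 25 per arm, the hypergeometric probabilities are:
- 3:2 split: 2 x 0.3257 = 0.651
- 4:1 split: 2 x 0.1493 = 0.299
- 5:0 split: 2 x 0.0251 = 0.050

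So 4:1 or worse has probability 0.35.

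A 4:1 split shifts the estimate by (4 - 1)/25 x g = 0.12 x g, which is 0.006, 0.012 and 0.024 logMAR at g = 0.05, 0.10 and 0.20. The standard error is 0.12 x sqrt(2/25) = 0.034, so these are about 0.2, 0.35 and 0.7 standard errors.

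Fisher's test on the baseline table would not flag this: p = 0.35 for 4:1 and p = 0.0502 for 5:0.

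**Precision, gross.** The share of variance due to diagnosis is R2 = q(1 - q)g²/0.0144.

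**Cost of adjusting.** With x of K such eyes in one arm, the squared correlation of diagnosis with arm is r² = (2x - K)²/(K(50 - K)), and the treatment variance is multiplied by 1/(1 - r²). For K = 5 the factor is 1.0045 (3:2), 1.042 (4:1) or 1.125 (5:0). The average is 0.651 x 1.0045 + 0.299 x 1.042 + 0.050 x 1.125 = 1.022. For K = 10 the average is also 1.022. Residual degrees of freedom fall from 47 to 46. I allow a factor of 47/46 for this, which is cautious, since the change in the t critical value alone costs only about 0.1%.

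**Net variance ratio, adjusted over planned:**

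| Share | Gap | R2 | (1 - R2) x 1.022 | also x 47/46 |
|---|---|---|---|---|
| 10% | 0.05 | 0.016 | 1.006 | 1.03 |
| 10% | 0.10 | 0.063 | 0.96 | 0.98 |
| 10% | 0.15 | 0.141 | 0.88 | 0.90 |
| 10% | 0.20 | 0.250 | 0.77 | 0.78 |
| 20% | 0.05 | 0.028 | 0.993 | 1.015 |
| 20% | 0.10 | 0.111 | 0.91 | 0.93 |
| 20% | 0.15 | 0.250 | 0.77 | 0.78 |
| 20% | 0.20 | 0.444 | 0.57 | 0.58 |

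If diagnosis is not prognostic at all, the ratio is 1.022, or 1.04 with the cautious allowance.

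**Power for 0.12 logMAR.** Before the cost of adjusting, the 93.4% would become 93.7% (10%, 0.05), 94.7% (10%, 0.10) or 95.7% (20%, 0.10). If 0.12 is instead a within-diagnosis SD, the planned model has 93.0%, 91.9% and 90.8% in the same cases.

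**The case against.** The strongest reply is that nothing here is an error. Randomisation supports the comparison, and the permutation test protects its type I error whether or not diagnosis is modelled. ANCOVA on the baseline value of the outcome is a standard choice for 50 eyes. This stands. A reader might infer that the primary result would be biased or the test invalid; the documents do not support that.

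A reader might also infer that an uneven split is likely. With 5 eyes, 65% of randomisations give 3:2, the most even split possible.

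Nor do the documents support a claim that the omission leaves the trial underpowered. On the SAP's inputs power is 93.4%, and under moderate assumptions it moves by a few points at most.

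The gain also rests on assumed values. A gap of 0.20 is 1.7 times the SAP's whole SD (0.20/0.12). Protocol section 3.2.2 excludes visually significant scarring, anterior chamber lenses, extensive synechiae, uncontrolled glaucoma and macular or optic nerve disease, so the bullous keratopathy eyes that remain are a restricted group and large gaps are harder to assume. This too stands, and the lower rows of each block in the table are upper cases.

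The objection does not remove the gap in the plan. Baseline acuity covers only part of any disease difference and may be dropped. The baseline tests lead to no correction, and influence analysis looks for unusual eyes rather than imbalance between arms.

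**Conclusion.** The point holds as a modest, inexpensive improvement and not as a defect in validity. Diagnosis is known for every eye before randomisation and appears in no stratum and no model. What remains of its effect after baseline acuity adds to the error, and an imbalance in that part goes uncorrected in the one trial that is run.

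At an assumed 0.10 gap the net reduction in variance is about 2% (10% share) to 7% (20% share), and a 4:1 split among 5 eyes moves the estimate by 0.012 logMAR, a tenth of the 0.12 target. Over the whole assumed range the net change runs from about +3% to -22% at a 10% share and from +1.5% to -42% at a 20% share. At a gap of 0.05 nothing useful is gained. The disease mix, the gap and the reading of 0.12 as a mixed SD are all assumptions that the documents cannot confirm. Prespecification is worthwhile because the possible loss is small, about 2 to 4% of variance, and the possible gain is larger.

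**What to change.** Before unmasking, change SAP section 4 so that the primary covariates are baseline BCVA, diagnosis (Fuchs versus pseudophakic bullous keratopathy) and treatment group, and keep the permutation p-value.

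Add a rule based only on baseline counts and fixed in advance: if the smaller class is very small, for example fewer than 5 eyes, the planned model stays primary and the diagnosis-adjusted model is reported as a sensitivity analysis. This keeps a primary coefficient from resting on a few eyes.

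Apply the same rule to the 3-month BCVA analysis and the 3- and 6-month mixed model in section 5. Extending it to the cell-count model is optional. That model holds no recipient characteristic, but no magnitude has been shown for that outcome.

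The cost is a sentence or two of SAP text, one degree of freedom and no new data, with a slight loss of precision if diagnosis proves not to be prognostic.
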